To support YBCS-HCP interactions, one HCP is nominated by each YBCS participant to receive the same study materials as their patient. Following eligibility screening and consent online or by paper, HCP participants whose YBCS patients are randomized to the intervention arm will receive access the full web-based educational intervention; HCP participants whose YBCS patients are randomized to the waitlist control arm will receive access to the list of curated web-based resources. HCP participants will complete an enrollment and a 24-week questionnaire. The UC San Diego institutional review board approved all study procedures, and the trial was registered at clinicaltrials.gov (NCT02667626).

Intervention prototype development and refinement

In line with community-based participatory research [22], a stakeholder panel was formed to design and conduct the study. The panel was comprised of 2 YBCS advocates and 6 investigators with clinical and research expertise in reproductive health, primary care, breast oncology, health behavior and randomized trials. To develop the intervention, we conducted systematic reviews and searched professional medical society guidelines for evidence on managing hot flashes and sexual health, addressing contraception needs and predicting fertility potential [23–25]. Supplemented by clinical expertise and review of existing web-based resources from professional medical societies and cancer advocacy groups, these evidence- and guideline-based practices were summarized into the SCP-R prototype. SCP-R was designed to improve self-efficacy by providing both up-to-date evidence and actionable steps for symptom management. The multi-level intervention further promoted taking actionable steps by incorporating reinforcement from the YBCS' HCP.

Seven focus groups with 37 YBCS were conducted to refine the content and presentation of the SCP-R [26]. For the intervention arm, we initially planned to provide each participant with only the SCP-R sections relevant to her specific reproductive issue(s). Based on focus group feedback, we changed the intervention design to allow participants in the intervention arm to access to all SCP-R sections.

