At enrollment, each YBCS participant nominates a HCP with whom they wish to discuss reproductive health issues. Study staff contact nominated HCPs by email, phone and/or fax for study recruitment. After five contacts, non-responsive HCPs are mailed the study consent, enrollment questionnaire and their patient's SCP materials. Interested HCPs are directed to the study web portal to create a secure personal account, followed by online access to study description, screening for eligibility and consent. Consented HCP participants complete the enrollment questionnaire and are provided with access to their patient's intervention materials, i.e. full SCP-R or only curated web-based resource lists. HCPs will complete a 24-week questionnaire and may opt to complete all study procedures (consent, questionnaires) and access intervention materials in a paper format.

Blinding

Study staff and YBCS and HCP participants are blinded to treatment allocation. Automated computer allocation of participants into intervention or waitlist control arm within the study portal allow for study staff to be blinded to assignment. YBCS and HCP participants are informed about participant randomization in the trial but are not notified of assignment until they complete their final study tasks. YBCS and HCP participants assigned to the waitlist control arm will be able to access the full SCP-R materials following completion of their final study tasks. Although 3 HCPs were nominated by more than one YBCS participant, each HCP only had participants in the same study arm.

YBCS outcome measures

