We will deploy several approaches to motivate YBCS participants to complete the study. Participants will receive up to \$100 in Amazon gift cards for completing each of 3 questionnaires and daily hot flash text messages. Weekly, automated reminder emails to complete study tasks will be sent via the web platform. Telephone call and/or text message reminders will be undertaken for overdue tasks for up to 5 contacts. On hot flash text messages, daily reports will be generated to monitor responses and identify those who had not responded in \geq 3 consecutive days for study staff contact.

HCP participant adherence and retention

HCP participants will receive up to \$40 in Amazon gift cards for completing each of 2 questionnaires. Weekly, automated email reminders to complete study tasks and view their patient's SCP will be sent via the website platform. HCPs who opted to participate via paper materials will be contacted by telephone calls to their medical practice to confirm receipt and encourage completion overdue tasks for up to 5 contacts. If a final questionnaire is not received within two months of mailing, questionnaires will be resent.

Statistical Analysis

The primary analysis will be intent-to-treat. The primary composite outcome will be an improvement in at least one reproductive health issue over the 24 week study, defined as: $\geq 50\%$ improvement in enrollment hot flash score, $\geq 50\%$ improvement in enrollment vaginal atrophy symptom score, use of highly effective contraceptive methods (sterilization, long-acting reversible contraception, injectables, pills, patch or vaginal ring), and fertility and pregnancy concern subscale scores <3. Logistic regression models will be used to test for differences by intervention versus control arm; odds ratios with 95% confidence intervals for intervention effect will be reported.

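### The waitlist release rule does not wait for the linked patient or provider, so a control HCP can see the full SCP-R before giving the 24-week ratings

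*Combined protocol and SAP*

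**What the plan says.** - **Release of materials (Blinding).** "YBCS and HCP participants assigned to the waitlist control arm will be able to access the full SCP-R materials following completion of their final study" […].
- **Disclosure of assignment (Blinding).** Patients and HCPs know that the trial is randomized but "are not notified of assignment until they complete their final study tasks".
- **Linkage (Material and Methods).** "one HCP is nominated by each YBCS participant to receive the same study materials as their patient".
- **Role of the HCP (Intervention prototype development and refinement).** "The multi-level intervention further promoted taking actionable steps by incorporating reinforcement from the YBCS' HCP".
- **HCP recruitment (HCP eligibility, recruitment, consent, enrollment and procedures).** HCPs are approached once the patient has named them. "After five contacts, non-responsive HCPs are mailed the study consent, enrollment questionnaire and their patient's SCP materials".
- **Late returns (the two adherence and retention sections).** For HCPs on paper: "If a final questionnaire is not received within two months of mailing, questionnaires will be resent". Overdue patient tasks are chased for up to five contacts, with no stated cut-off.
- **Shared HCPs (Blinding).** "3 HCPs were nominated by more than one YBCS participant", each with patients in one arm only.
- **Outcomes.** Patients supply the primary composite. HCP preparedness and confidence are secondary outcomes compared between arms (Statistical Analysis).

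**The concern.** Exposure is delivered to a linked pair, and both members supply outcomes, but the release rule names only the completion of tasks and puts no condition on the other member. Patients nominate an HCP with whom they want to discuss these issues, so passing material within the pair is what the design encourages.

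Three orderings leave an outcome open after a linked person's release:

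- **(a) Control patient first.** She learns her arm, receives the full SCP-R and can take it to her HCP before the HCP's 24-week ratings. This is the main route, and it affects a secondary comparison.
- **(b) Control HCP first.** The HCP receives the full SCP-R while the patient's 24-week questionnaire is overdue.
- **(c) Shared control HCP.** The HCP receives the full SCP-R while another of the HCP's control patients is still in follow-up.

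Exposure of controls mainly biases toward no effect. Separately, in either arm, a member who has been told the assignment can reveal it to the other, whose self-report could then move in either direction.

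**Working it through.** **1. Is there a pair-level condition?** No. Both Blinding statements refer to the completion of final study tasks, and no other section adds that the linked person must have finished. The same-arm statement on shared HCPs rules out sharing across arms; it does not prevent early release among control patients of one HCP.

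**2. Can pair members finish at different times?** Yes. The start of the HCP's 24 weeks is not defined, and either reading leaves a gap:

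- If it starts at HCP enrolment, an HCP recruited after the patient's randomization is due after her, and route (a) is open.
- If it follows the patient's timeline, the two are due together and the order depends on who answers promptly. A slow HCP opens route (a); an overdue patient opens route (b).

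**3. HCP comparison.** Let p be the share of control HCPs exposed before their ratings. If exposure gives the full effect (an upper bound), observed difference = true difference × (1 − p). The documents give neither p nor a target difference. Assuming 20 percentage points in the proportion prepared:

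| Assumed p | Observed difference |
|---|---|
| 10% | 20 × 0.90 = 18 points |
| 25% | 20 × 0.75 = 15 points |
| 40% | 20 × 0.60 = 12 points |

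**4. Primary composite.** Inputs from Sample size: 50 per arm, 25% versus 52%, 80% power; two-sided alpha 0.05 is stated for the t-test and assumed here.

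Reproducing the plan's figure: mean rate (0.25 + 0.52)/2 = 0.385; null SE = √(2 × 0.385 × 0.615/50) = 0.0973; alternative SE = √((0.25 × 0.75 + 0.52 × 0.48)/50) = 0.0935; z = (0.27 − 1.96 × 0.0973)/0.0935 = 0.85, so power is 80.2%. The stated 80% reproduces.

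Let f be the share of control patients who gain the full 27-point benefit before their outcome is collected (again an upper bound per exposed patient). The control rate becomes 0.25 + 0.27f. The plan's 157 randomized, after 20% drop-out and a design effect of 1.2, leave 157 × 0.8/1.2/2 = 52.3 effective per arm.

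| Assumed f | Control rate | Power, 50 per arm | Power, 52.3 per arm |
|---|---|---|---|
| 0 | 25.0% | 80.2% | 82.0% |
| 2% | 25.5% | 78.4% | 80.2% |
| 5% | 26.4% | 75.5% | 77.5% |

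**5. How large could route (c) be?** Three shared HCPs with more than one patient each means at least 3 × 2 = 6 patients, or 6/157 = 3.8% of those randomized. With exactly two each, only the later patient of each HCP is exposed: at most 3 of about 157/2 = 78.5 controls, again 3.8%, and only if all three HCPs are in the control arm and gaps in enrolment allow it. The documents state neither their arms nor the number of patients each has.

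**The case against.** The strongest reply is that the plan leaves the trigger unspecified and does not actually choose person-level release. The word their could be read for the pair, and the portal already pairs patients with HCPs (Website and text messaging platforms). Person-level reading is the plain one, but the reply stands to this extent: the text shows an open route, not that contamination occurs.

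Several stronger readings are tempting and are not supported:

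- **That control patients usually finish first.** No lag is given, and the HCP's start point is undefined. Routes (a) and (b) need opposite orderings, so within a pair they cannot both apply.
- **That two months is the lag.** It is the point at which an unreturned mailed questionnaire is sent again, and it falls after the final mailing. An HCP who never returns it gives missing data, not contaminated data.
- **That route (b) exposes patients during the 24 weeks.** A patient chased for an overdue final questionnaire is already past week 24, and her daily hot-flash reports already cover that period. Only items collected late are at risk.
- **That the three shared HCPs are controls, or that three patients per provider is expected.** The arms are not stated, nominated does not mean enrolled, and the average of three is the plan's worst case.

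Exposure also needs a chain of events: the materials are opened, passed on, read, and change a rating, all before the questionnaire is returned. The full-effect figures are therefore ceilings. Finally, making every control patient wait for all patients of a shared HCP could delay her by months; that objection is sound, and the remedy below avoids it.

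**Conclusion.** The concern holds as a gap in the release rule. As written, assignment is disclosed and the full SCP-R opened to controls without regard to whether the linked person's outcome is in. The main consequence is possible dilution of the secondary HCP preparedness and confidence comparison.

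The effect on the primary composite is probably small, because it needs either an overdue patient whose HCP finished first or one of the few shared HCPs. A reader might infer that the trial's primary power is seriously eroded; the documents do not support that.

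The size is unknown. Every attenuation and power figure above rests on an assumed exposure rate and on full benefit in each exposed person. The case for acting is that the remedy is cheap, not that the damage is shown to be large.

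**What to change.** 1. **To a patient:** disclose assignment (both arms) and release the full SCP-R (controls) only when she has finished and her own enrolled HCP has submitted the 24-week questionnaire or passed a fixed closing date.
2. **To an HCP:** do so only when the HCP has finished and all of that HCP's enrolled patients have submitted theirs or passed the closing date.
3. Apply the same rule to paper mailings.
4. Define the start of the HCP's 24 weeks, including for an HCP with more than one patient.
5. Record release dates, and add a sensitivity analysis that excludes outcomes collected after a linked person's release.

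**Cost.** A changed portal trigger using pairing that already exists, a matching step for paper HCPs, and a few sentences in the protocol. The sample size does not change. Some controls wait longer for the full materials, limited by the closing date. A patient does not wait for other patients of a shared HCP. That leaves a small residual route, since a released patient could still show the materials to a shared HCP; the recorded dates let the sensitivity analysis cover it.

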YBCS are eligible if they report experiencing at least one of the four targeted reproductive health issues: hot flashes (\geq 4 per day with \geq 1 at least moderate in severity), moderate to high pregnancy and/or fertility concerns (fertility or pregnancy subscale score >3 on the Reproductive Concerns After Cancer Scale), not using contraception or using a less effective method (barrier or fertility awareness methods, withdrawal, or spermicides), or vaginal atrophy symptoms (\geq 1 symptom of vaginal dryness, irritation, soreness or dyspareunia over the past 4 weeks reported as at least moderate in severity). Additional eligibility criteria include: ages 18-50 at study enrollment, diagnosed with stage 0-III breast cancer between ages 18-45, completed primary cancer treatment including surgery, chemotherapy and radiation, are not pregnant at enrollment, are able to read English and access the Internet, and are able to complete daily text message hot flash diaries.

YBCS are recruited from the following sources: (1) cancer advocacy organizations including the Young Survival Coalition, Susan G. Komen San Diego and Army of Women-a program by the [name] Research Foundation, (2) referrals from health care providers and patient advocates, (3) Research Match, (4) previous observational studies conducted by the investigators. Interested YBCS are directed to the study web portal to create a secure personal account, followed by online access to study description, screening for eligibility and consent.

Consented participants complete the enrollment questionnaire and undergo a 7-day daily hot flash text message run-in period. Participants receive two daily text messages prompting them to report the number of hot flashes and severity of each hot flash (mild, moderate, severe, or very severe) in the previous 24 hours. Participants with at least 70% adherence over 7 days are then randomized.

YBCS randomization

Computerized, blocked randomization with equal allocation to intervention and waitlist control arms was undertaken. Randomization is stratified by the four a priori reproductive health issues in order to

maintain balance between the intervention and waitlist control groups with regard to these factors. Fifteen unique strata were created based on possible combinations of experiencing one or more of the four late effects.

HCP eligibility, recruitment, consent, enrollment and procedures

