Hot flash frequency and severity over the prior 24 hours will be measured in each questionnaire and via daily via text messages using the following questions: "How many hot flashes have you had in the past 24 hours?" and "How many of your hot flashes in the past 24 hours would you categorize as mild, moderate, severe and/or very severe?" The hot flash score is calculated as the weighted sum of the number of hot flashes in each severity category multiplied by a severity-exclusive weight (1-mild, 2-moderate, 3-severe, 4-very severe). For the primary analysis, a decrease of 50% in the hot flash score will be defined as an improvement in hot flashes for the primary composite outcome. Secondary hot flash outcomes will include quality of life measured by the 29-item Menopause-specific Quality of Life (MENQOL) scale, confidence to talk with a HCP about hot flash management, plans to implement and implementation of a suggested tip from the intervention materials.

Fertility-related concerns will be measured with the Reproductive Concerns After Cancer Scale (RCAC), specifically fertility potential and pregnancy subscales. The RCAC is an 18-item multidimensional scale composed of 6 subscales (fertility potential, pregnancy, child's health, disclosure to partner of fertility status, personal health, acceptance of infertility) measuring reproductive health concerns of young adult female cancer survivors. The two subscales were chosen, because the SCP-R content addressed these constructs. Each subscale consists of 3 questions with response options ranging from 1 "Strongly disagree" to 3 "Neither agree nor

disagree" to 5 "Strongly agree". Scores for the fertility and pregnancy subscales will be calculated by averaging responses (range 1-5), scores > 3 indicating concern. For the primary analysis, scores \leq 3 in follow up will be considered an improvement in fertility-related concerns for the primary composite outcome. Secondary fertility-related outcomes will include the overall RCAC score, referral, consultation and treatment with a fertility specialist, pregnancy planning, and confidence to talk with a HCP about fertility-related concerns and plans to implement and implementation of suggestions from the fertility SCP.

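### The primary composite has two fertility cut-offs (≤3 and <3) and does not limit scoring to issues present at enrollment, so unchanged women can count as improved

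*Combined protocol and SAP*

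**What the plan says.** The Statistical Analysis section defines the primary composite as "improvement in at least one reproductive health issue over the 24 week study" and lists four components.

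- **Fertility, YBCS outcome measures:** "scores \leq 3 in follow up will be considered an improvement in fertility-related concerns for the primary composite outcome". The same paragraph gives the scale ("Each subscale consists of 3 questions with response options ranging from 1" to 5, averaged) and defines concern: "scores > 3 indicating concern".
- **Fertility, Statistical Analysis:** "fertility and pregnancy concern subscale scores <3".
- **Fertility, entry criterion** (YBCS eligibility, recruitment, consent and enrollment): "fertility or pregnancy subscale score >3 on the Reproductive Concerns After Cancer Scale".
- **Hot flash and vaginal symptoms:** a reduction of at least 50% from the enrollment score, for example "improvement in enrollment vaginal atrophy symptom score".
- **Contraception:** use of a highly effective method during follow-up, analyzed in women at risk of unintended pregnancy (defined by anatomy, sexual activity and age ≤45).

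One issue is enough for entry: "YBCS are eligible if they report experiencing at least one of the four targeted reproductive health issues". Randomization is stratified by the 15 possible combinations of the four issues.

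**The concern.** Three gaps in the primary outcome rule leave its coding open.

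1. **Two cut-offs.** A follow-up score of exactly 3.0 is an improvement in one section and not in the other. Under <3, such a score is neither a concern nor an improvement.
2. **One subscale or both.** Entry needs either subscale above 3. The Statistical Analysis section joins the two with *and*; the outcome section says only *scores*. If one subscale were enough, a woman who entered on one with the other already ≤3 would be a responder on the day she enrolled.
3. **No link to enrollment status.** Two components are measured against the enrollment score. Fertility and contraception are not, and no sentence confines any component to women who had that issue at entry. The at-risk restriction narrows the contraception component but does not remove women already using a highly effective method.

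At stake is whether the same data give one primary result or several, depending on who writes the code. Under the third gap, women who count as improved without change enter both arms equally, pull the odds ratio toward 1 and cost power.

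**Working it through.** **Can a score of 3.0 occur?** Three items with five options give 5³ = 125 answer patterns. Of these, 19 sum to 9 and so average 3.0, including the middle option on all three items. This counts patterns, not women.

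**Who can count without change?** Of the 15 strata, 7 have no fertility issue. By the entry criterion, women in those strata have both subscales ≤3 at enrollment. Under the ≤3 rule they meet the fertility component unless a concern arises.

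**The plan's own power.** The Sample size section gives 25% control, 52% intervention, 50 per arm and 80% power. Two-sided alpha 0.05 is stated there for the t-test and assumed here for the composite. With the pooled two-proportion z test and p̄ = (0.25 + 0.52)/2 = 0.385:

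z = [0.27·√50 − 1.96·√(2·0.385·0.615)] / √(0.25·0.75 + 0.52·0.48) = (1.909 − 1.349)/0.661 = 0.848, so power is 80.2%. The stated figure reproduces. The planned odds ratio is (0.52/0.48)/(0.25/0.75) = 3.25.

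**Effective sample size behind the target.** 157 randomized, less 20% drop-out, divided by the design effect 1.2, over two arms: 157 × 0.8/1.2/2 = 52.3 per arm, where power is 82%.

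**Reading A: 25% and 52% apply to the other women.** Let q be the share counted as improved without change (assumed; not in the documents). The rates become q + (1 − q)·0.25 and q + (1 − q)·0.52.

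| q | Control | Intervention | Odds ratio | Power, 50/arm | Power, 52.3/arm |
|---|---|---|---|---|---|
| 0 | 25.0% | 52.0% | 3.25 | 80% | 82% |
| 5% | 28.8% | 54.4% | 2.96 | 75% | 77% |
| 10% | 32.5% | 56.8% | 2.73 | 69% | 71% |
| 20% | 40.0% | 61.6% | 2.41 | 58% | 60% |

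**Reading B: 25% and 52% already include these women.** Stated power is unchanged and q cannot exceed 25%. The other women must then show (0.25 − q)/(1 − q) versus (0.52 − q)/(1 − q): 16.7% versus 46.7% at q = 10% (30 points) and 6.3% versus 40.0% at q = 20% (34 points), rather than 27 points.

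**Cost of restricting scoring to enrollment issues.** Entry allows ages 18 to 50, but the contraception outcome stops at 45 and requires a uterus and an ovary. Let r be the share (assumed) who entered only through contraception and fall outside that group, so that they cannot respond. The rates become (1 − r)·0.25 and (1 − r)·0.52. Power at 50 per arm is 77%, 73% and 65% for r = 5%, 10% and 20%.

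**The case against.** **Intent.** The study aims to improve issues that participants experience, eligibility defines those issues by thresholds, and randomization is stratified by them. Improving an issue presupposes having it. This is fair, and a baseline restriction was probably intended. But the outcome section itself defines a follow-up score as the improvement, and no sentence adds the restriction. Intent also cannot settle ≤3 against <3.

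**Both subscales.** The most natural reading of both sections is that both must meet the cut-off. This largely stands. The second gap is conditional on the other reading, and one added word would close it.

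**Size.** The cut-off conflict affects only scores of exactly 3.0, whose frequency is unknown, and q and r are assumed. The design effect is described in the plan as a worst case, and the Blinding section reports only three providers nominated by more than one participant. Without it, 157 × 0.8/2 = 62.8 per arm, and power is 88% at q = 0, 79% at 10% and 68% at 20%. Imputation of missing outcomes may soften the drop-out loss further. These points temper the figures, but the loss at a given q remains, and the design effect is the plan's own allowance.

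**Other open points.** The plan also does not say whether week 12, week 24 or either counts, or whether the composite's hot flash score comes from the questionnaires or the daily texts, and its two contraceptive lists are worded differently. These are separate gaps and do not weaken this one.

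**Conclusion.** The concern holds, and the primary outcome rule must be corrected. The conflict between ≤3 and <3, and the absence of any restriction to enrollment issues, can be read directly from the text and need no assumption. Followed literally, the text counts some unchanged women as improved.

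The consequence of the missing restriction is dilution in both arms, not bias between them. Its size is unknown, because the documents give neither the share of women who would count without change nor the share scoring exactly 3.0. Under Reading A, shares of 5% to 20% would lower power at 50 per arm from 80% to between 75% and 58%; under Reading B, stated power stands but the required effect in the other women grows. These figures illustrate what is at stake; the need for correction rests on the wording.

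**What to change.** Put the following rule in the Statistical Analysis section:

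> A participant is a composite responder if at least one issue flagged for her at enrollment (the stratification flags) meets its improvement rule. Issues absent at enrollment are not scored. All randomized women stay in the denominator.

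Use ≤3 in both sections, since it is the complement of the plan's >3 definition of concern. State whether one or both subscales must meet it. Requiring both is the exact complement of the either-subscale entry rule and means that no concern remains on either.

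Make the change as a dated amendment before unblinded outcome data are seen; the sections on randomization and blinding already describe randomization and provider nominations in the past tense.

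Report by arm how many women entered only through contraception but fall outside the at-risk group. As a sensitivity analysis, repeat the model without those identifiable from enrollment data (age, uterus and ovaries).

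The cost is text only: the flags already exist for stratification, and eligibility and randomization do not change. Responder rates will be lower in both arms, and the contraception-only women outside the at-risk group cannot respond. Their number is not in the documents, which is why it should be reported.
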